## 3. Eligibility Criteria

Subject inclusion criteria for RA blood:

1. Must meet 1987 Revised Criteria for the Classification of Rheumatoid Arthritis defined as the diagnosis of the referring physician.

2.. Persistent knee swelling (>ARA grade 2) for 2 weeks, and no recent intra-articular corticosteroid injection.

3. Age 18 years and older.

#### 4. Exclusion Criteria:

1. Patients having received intra-articular corticosteroid joint injection within the last 2-4 weeks.

- 2. Patients with active systemic or joint infections.
- 3. Women who are pregnant (pregnancy status will be self-reported)
- 4. Patients under 18 years of age
- 5. Non-English speakers

#### 5. Vulnerable Population Inclusion:

- 1. No vulnerable population will be included in this study.
- 2. RA patients treated with Cimiza have to practice abstinent.

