#### 8. Special Precautions to be Taken by Researchers

The potential risks are limited to that associated with routine blood draw, and the collection and storage of personal health information.

A possible risk of the research is that your participation in the research or information about you and your health might become known to individuals outside the research.

[name] will obtain consent from patients with an informed consent document and authorization form. Copies of these forms will be added to each patient's permanent medical record. Drawn peripheral blood samples will be stored and a assigned a code, which will be identifiable only by the master list. The master list will be kept in a locked cabinet or a computer that would need a password to be accessed. Besides the PI and the key personnel, nobody will have access to the locked cabinet or the computer where the information is stored. The consent forms, authorization forms, and the coded index will be only available to the PI and key lab personnel involved in the project. The consent forms and authorization forms will be kept in a locked cabinet. The data will be kept on a secured server accessible only to the PI and key lab personnel involved in the project. The data recorded in the lab books and computer records will refer to the subject's code, not the name. Data shared with collaborators will be identified only by the code. The patients will never be identified in any publication.

When the results of the research are published or discussed in conferences, no information will be included that would reveal your identity.

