## 11. Potential Risks and Benefits to Subjects

The risks associated with blood draw include fainting, pain, a bruise at the site of vein puncture, inflammation of the vein. Every care will be taken to avoid these complications. The side effect of the drug Cimzia are similar to other 3 TNF-blockers these include serious infections, Invasive fungal infections, cases of lymphoma and other malignancies, Heart failure, Hepatitis B virus reactivation and Lupus-like syndromes.

Use of Cimzia may cause damage to the fetus. Therefore, it is recommended that patient practice abstinence.

Measures taken to minimize these risks are detailed above in #8. Samples and clinical information will be stored and cared for with every precaution taken to ensure confidentiality of participant information. There will be no compensation except for a parking sticker and testing results will not be released to individual subjects. However if the patients require to be treated with Cimzia (anti-TNF $\alpha$ ), the medication will be provided to them free of charge up to 2 years. Subjects will not benefit directly, but receive medication.

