## 12. Monitoring and Safety of Subjects

Possible adverse events that could be anticipated would be either complications arising from obtaining blood samples or breach of data security. While these events are unlikely, they would be immediately reported to the IRB. As above, all precautions will be taken to avoid adverse events, and any improvements in the sample collection and archival process that become available during the course of the study will be implemented (for example, new technology that allows the study of smaller amounts of blood sample, new widely available data security measures, etc.) Referring physicians will be charged with the continued monitoring of study participants as part of their routine care.

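### Section 11 names fetal harm from Cimzia and points to Section 8 for the safeguards, but Section 8 leaves out all drug risks, Section 12 names no drug event, and the pregnancy self-report has no stated timing

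*Combined protocol and SAP*

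**What the plan says.** Four parts of the combined protocol and SAP bear on this.

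- **Abstinence.** Section 5 makes it a condition: "RA patients treated with Cimiza have to practice abstinent". Section 11 gives the reason, "Use of Cimzia may cause damage to the fetus", and then softens the rule: "Therefore, it is recommended that patient practice abstinence".
- **Risk measures.** Section 11 lists the drug's serious risks (infection, malignancy, heart failure and others) and says "Measures taken to minimize these risks are detailed above in #8". Section 8 opens with "The potential risks are limited to that associated with routine blood draw, and the collection and storage of personal health information". The rest of Section 8 deals with consent, coding, storage and access.
- **Adverse events.** Section 12 says "Possible adverse events that could be anticipated would be either complications arising from obtaining blood samples or breach of data security" and that "they would be immediately reported to the IRB". It leaves continued monitoring to the referring physicians in routine care.
- **Pregnancy status and exposure.** Sections 4 and 9 exclude pregnant women by self-report and give no time for it. Section 2 plans 200 donors, of whom 150 do not respond to DMARDs, transfer to the second group and receive Cimzia supplied through the study. Their blood is drawn at the onset of the study and at 3 and 6 months on Cimzia. Section 11 adds that "the medication will be provided to them free of charge up to 2 years".

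**The concern.** The protocol names a risk to the fetus, makes abstinence a condition of the drug, and points to a section that should hold the protective measures. That section does not hold them, and its opening sentence contradicts the risk list that refers to it. A site reading Section 8 or Section 12 alone would conclude that the study carries no drug risk to manage or report.

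What is at stake is participant safety. A woman could begin supplied Cimzia, or continue it, without a stated step that asks about pregnancy at that time. If a pregnancy occurred on the drug, no stated step would carry it from the treating physician to the PI and the IRB. The analysis of IL-7 and IL-7R is not touched.

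**Working it through.** The plan gives no figure on this point to reproduce. The check sets the sections side by side and adds a little arithmetic on exposure and cost.

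**1. The cross-reference.**

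| Item | Section 11 | Section 8 |
|---|---|---|
| Blood-draw risks | listed | named as a risk |
| Health information | confidentiality precautions stated | named as a risk, with measures |
| Serious Cimzia risks | listed | absent |
| Fetal harm | stated | absent |
| Measures to reduce these risks | referred to Section 8 | only consent, coding, storage and access |

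Section 8's opening sentence and Section 11's list cannot both be right. Both sections are readable in full, so this finding does not depend on any page that was unavailable.

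**2. Event reporting.** Section 12 anticipates two kinds of event and sends those to the IRB. Neither is a drug event, and pregnancy is not named. The section does not say that other events go unreported.

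**3. Abstinence.** A patient who abstains satisfies both Section 5 and Section 11. A patient who does not abstain breaks Section 5 but only departs from advice under Section 11. The two sections therefore differ in force, and applying the stricter one removes the difference.

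**4. Timing of the self-report.** Inputs: 200 donors, 150 on Cimzia, draws at 3 and 6 months (Section 2); supply up to 2 years (Section 11).

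- Share of donors planned to receive the drug: 150 / 200 = 75%.
- Reading A: donors enter group 1, fail DMARDs and then transfer. If the self-report is taken only at entry, it predates the first Cimzia dose by an interval that the plan does not bound.
- Reading B: group 2 patients enrol when Cimzia starts. The self-report may then fall close to the first dose.
- On either reading, the available text ties no self-report to the 3 or 6 month draw.
- If supply begins with the first dose and lasts the full period, it continues 24 − 6 = 18 months past the last planned draw.

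The documents do not give the number of women who could become pregnant, so no count of exposed pregnancies can be derived.

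**5. Size of the added work.** Three time points (first dose, month 3, month 6) × 150 donors = 450 answers as an upper bound. The real number is lower, because only women who could be pregnant are asked.

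**The case against.** The other side has a fair case.

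- *The abstinence conflict is editorial.* This stands. Section 5 gives staff a rule, and following it satisfies Section 11 too.
- *The missing provisions may exist elsewhere.* Section 7 and the consent pages were not available, and Section 13 says that the consent form describes the study. This stands for every statement of absence about timing and pregnancy reporting. It does not rescue Section 8, which is wrong as written whatever those pages contain.
- *The outdated self-report is inferred.* A reader might infer that transferred donors will start Cimzia on an old pregnancy report. The documents do not support that. Section 2 fits either reading, no interval is given, and nothing says that the exclusion is applied only once. It remains a possibility that the plan does not close.
- *Cimzia is an approved drug in standard use, and the treating physician monitors the patient.* This lessens the concern, since a pregnancy may well be noticed in routine care. It does not remove it, because the study supplies the drug and names the fetal risk itself. Section 16 also foresees no further research role for the physician after the routine care that yields the specimens, so no stated step takes the information to the PI.
- *Sections 8 and 12 omit all drug risks, not only pregnancy.* This is true. The correction to Section 8 should therefore cover the whole list in Section 11.

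A reader might also infer that pregnancies on the drug would go unreported, or that the plan ignores pregnancy altogether. Neither follows: Section 12 does not exclude other events, and pregnancy is an exclusion in Sections 4 and 9.

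**Conclusion.** The point holds, with unequal strength across its parts.

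- **Firm:** Section 11 refers to Section 8 for measures that are not there, and Section 8's statement of the risks contradicts Section 11. Section 12 names no drug event.
- **Firm but minor:** abstinence is required in one section and recommended in another.
- **Conditional:** the pregnancy self-report could predate the first supplied dose. This assumes that donors transfer from group 1 after some delay, that the report is not renewed at transfer, and that neither Section 7 nor the consent form provides for it. It is possible, not demonstrated.

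A tally of planned contacts without a self-report would not measure the risk, because the choice of contacts belongs to whoever counts them. What can be said from the documents is that three-quarters of the donors are planned to receive the drug. The matter deserves correction because it concerns safety and is cheap to repair.

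**What to change.** 1. **Section 8:** replace the opening sentence so that it covers the Cimzia risks listed in Section 11, including harm to the fetus, and write in the pregnancy measure from item 3.
2. **Section 11:** use the required wording of Section 5 for abstinence, and check that the consent form agrees.
3. **Self-report:** repeat the existing question immediately before the first supplied Cimzia dose and at the 3 and 6 month draws.
4. **Section 12:** add pregnancy on supplied Cimzia as an event that the referring physician passes to the PI for reporting to the IRB. Section 16 should allow for this one step.

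The cost is wording edits and up to three extra answers per woman who could be pregnant. No new test, visit or member of staff is needed. These checks do not cover supply after month 6. The available text describes no later study contact to which a further check could be attached, so the sponsor should decide separately how that period is handled.

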## 6. Probable Duration of Protocol

The samples will be stored for 10 years or until total sample depletion.

#### 8. Special Precautions to be Taken by Researchers

The potential risks are limited to that associated with routine blood draw, and the collection and storage of personal health information.

A possible risk of the research is that your participation in the research or information about you and your health might become known to individuals outside the research.

[name] will obtain consent from patients with an informed consent document and authorization form. Copies of these forms will be added to each patient's permanent medical record. Drawn peripheral blood samples will be stored and a assigned a code, which will be identifiable only by the master list. The master list will be kept in a locked cabinet or a computer that would need a password to be accessed. Besides the PI and the key personnel, nobody will have access to the locked cabinet or the computer where the information is stored. The consent forms, authorization forms, and the coded index will be only available to the PI and key lab personnel involved in the project. The consent forms and authorization forms will be kept in a locked cabinet. The data will be kept on a secured server accessible only to the PI and key lab personnel involved in the project. The data recorded in the lab books and computer records will refer to the subject's code, not the name. Data shared with collaborators will be identified only by the code. The patients will never be identified in any publication.

When the results of the research are published or discussed in conferences, no information will be included that would reveal your identity.

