PB mononuclear cells will be isolated from RA whole blood and drawn into EDTA or CPT tubes and isolated by Histopaque gradient centrifugation. Monocytes will be isolated from RA PB mononuclear cells by negative selection (as shown in the preliminary data) and half of the monocytes will be differentiated to macrophages for 7 days. The expression levels for IL-7 and IL-7R will be determined by real-time RT-PCR and FACS analysis.

In our statistical analysis, we will first perform a stratified analysis to evaluate the differential expression levels in RA patients with active and inactive disease, controlling for the type of treatment. Data analysis will be performed in collaboration with an UIC Center for Clinical and Translational Science statistician. Specifically, we will perform the comparison of IL-7 and IL-7R expression among RA patients with active (DAS28>2.6) vs. inactive disease (DAS28<2.6) for DMARDs group (group 1). We will then perform a similar comparison for the DMARDs and Cimzia® therapy group (group 2). The stratified analysis can adjust for the potential confounding effect of treatment received and allows for the detection of the potential differential relationships between expression levels of IL-7 or IL-7R and disease status. We will also perform a pooled regression analysis in which the expression logarithm of IL-7 or IL-7R from patients is regressed on the treatment group indicator [DMARDs (group 1) versus on DMARDs plus Cimzia® therapy (group 2)] and disease status (active or inactive disease) which would demonstrate the interaction between treatment groups and disease activity. Such an analysis pools subjects from two treatment groups together and can therefore increase the sample size, and hence potentially the power of detecting the relationships between biomarkers and disease status. The RA samples will be collected over a 2 year period and the data will be analyzed in the last year of the proposal.

**Measure outcomes:** For any of the genes that demonstrate at least 2.5 fold increase (89% sensitivity calculated based on our preliminary data) in active disease compared to remission, correlation coefficient will be calculated for that gene expression level, rheumatoid factor, Cyclic Citrullinated Peptide Antibody (anti-CCP), C-Reactive Protein (CRP), DAS28 and disease duration.

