## 14. Procedures which will be used to Maintain Confidentiality of Research and Study Subject Materials

A number of procedures will be used to maintain confidentiality of subjects. At enrollment, each subject will receive a designated study code number. All consent forms will be stored in locked file cabinets.

All personal health information will be stored in a secure database which only the PI and designated research staff can access. This database will be password-protected, and will be stored in a computer or in a locked file cabinet. Coded numbers will be generated for each subject, and these coded numbers will be used to label each specimen. These coded numbers will be used to file the subject's clinical information in an independent clinical database which is free of protected health information. The clinical database will also be password-protected and stored on a computer in a locked office. Only the PI and her designated staff will have access to the secure databases with protected health information and the link between anonymous specimen code numbers and patient identifying information. Coded data may be shared with other investigators or included in publications, but no patient identifying information will be released. Every precaution will be taken to ensure confidentiality of patient information.

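### The plan does not mask the RT-PCR and FACS operators to DAS28 status, treatment group or visit, and its access and labelling rules would let them learn all three

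*Combined protocol and SAP*

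**What the plan says.** The laboratory outcome is set in section 2 (Protocol Methodology): "The expression levels for IL-7 and IL-7R will be determined by real-time RT-PCR and FACS analysis". The operators are not named. The same section compares expression in active and inactive disease within each treatment group, then in a pooled regression on log expression.

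Section 8 (Special Precautions) covers access. On the key, it says that "the coded index will be only available to the PI and key lab personnel involved in the project". On the data: "The data will be kept on a secured server accessible only to the PI and key lab personnel involved in the project". On records: "The data recorded in the lab books and computer records will refer to the subject's code, not the name".

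Section 14 (Confidentiality) covers labelling. Code numbers are generated per subject, and "these coded numbers will be used to label each specimen". It continues: "These coded numbers will be used to file the subject's clinical information in an independent clinical database". On identifiable data and the link to identity it uses a different term for those allowed in: "Only the PI and her designated staff will have access to the secure databases with protected health information".

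Section 2 also fixes the draws. DMARD patients in remission give one sample. Patients who go on to Cimzia give samples at onset, 3 months and 6 months.

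Both sections present coding as protection of confidentiality. Neither mentions masking of assay readers, and nor does any other section of the available text (section 7 was not available).

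**The concern.** A code protects a patient's identity from outsiders. It protects a measurement from the reader's expectations only if the reader cannot get from the code to the patient's status. Here the stated rules leave that route open, for three reasons that act together:

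- Treatment is open, and section 1 states a direction: expression is high in active disease and falls with response to anti-TNF therapy.
- The readouts involve some judgement. FACS needs gates and positivity cut-offs. RT-PCR is mostly read by the instrument but leaves discretion over repeats and exclusions. The plan fixes no rule for any of these.
- The comparison of interest is between groups whose status a reader could know.

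If knowledge of status influenced those choices, the error would fall on one side of the active-versus-inactive contrast. Unlike random assay error, it would not shrink as donors are added. It also could not be undone afterwards for choices, such as repeats and exclusions, already made with status known.

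**Working it through.** The plan has no figure to reproduce on this point. The check is mainly a reading of who can learn what, followed by an illustration of scale.

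**Routes from tube to status**

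1. *Through the clinical data.* Section 14 uses the same subject code on the specimen and in the clinical database. Anyone who can open that database can go from tube to clinical information without the index. Section 14 does not say who may open it. Section 8 opens the server holding the data to key lab personnel; if that server includes DAS28, the route is complete.
2. *Through the index.* As described, the index links code to person. It does not hold DAS28, so by itself it gives identity. Status follows only with a further look at records.
3. *Through the label.* Codes are per subject. DMARD remitters have one tube and group 2 patients have three. A second or third tube under the same code is therefore a 3- or 6-month sample from a Cimzia patient, recognisable without opening any file. This reveals group and visit, not DAS28, and an onset tube read on arrival is not exposed in this way.

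**Illustration of scale (assumed shifts; the documents give none)**

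Inputs: 50 donors who remit on DMARDs and 150 who do not (sections 2 and 9), compared at a two-sided 5% level. There is no true difference, and the readout in one group is shifted systematically by b standard deviations.

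- SE = √(1/50 + 1/150) = √0.02667 = 0.1633 SD
- False-positive rate = 1 − Φ(1.96 − b/SE) + Φ(−1.96 − b/SE)

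| b (SD) | b/SE | False-positive rate |
|---|---|---|
| 0 | 0 | 5% |
| 0.1 | 0.61 | 9% |
| 0.2 | 1.22 | 23% |
| 0.3 | 1.84 | 45% |
| 0.5 | 3.06 | 86% |

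On the fold scale, section 2 uses a 2.5-fold increase to decide which genes go on to correlation analysis. If active samples read 20% too high relative to remission, a true ratio of 2.5/1.20 = 2.08 would reach that threshold. If they read 10% too high, a true ratio of 2.5/1.10 = 2.27 would. The threshold only triggers correlation coefficients; it is not a success criterion.

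**The case against.** The best defence is that section 8 sets a confidentiality limit against outsiders and does not describe how assays are read. Lab books and computer records carry the code, so recorded lab work is already coded, and permission to open an index is not use of it at the cytometer. The readers are not named: section 8 speaks of key lab personnel and section 14 of designated staff, and neither is said to be the assay operators. The clinical database is separate and password-protected. RT-PCR leaves less to judgement than FACS, and the shifts used above are assumptions.

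Most of this stands, and it limits what may be claimed. A reader might infer that the endpoint is read unblinded; the documents do not say so. They permit access and are silent on masking. A reader might infer that the index shows disease status; as described, it links code to person. A reader might infer that masking would cost nothing because codes exist; the subject code does not hide repeat visits, and a key-holder who reads no assays is needed. A reader might also extend the point to a before-and-after contrast. Section 2 specifies no such analysis; it is only implied by the draw schedule and by the paired t test in section 10.

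The defence does not close the gap. Nothing stated would stop a reader from learning status, and the label by itself can reveal group and visit.

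**Conclusion.** The point holds as a gap in the plan with a concrete, low-cost remedy. It is not evidence of biased results. The access and labelling rules let key lab personnel reach the index and the study data, and no available text masks the operators to DAS28 status, group or visit. This leaves an avoidable route for bias in the active-versus-inactive comparison.

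The size is unknown. The illustration shows only that, with 50 against 150 donors, a systematic shift of a few tenths of a standard deviation would matter; it does not show that any shift occurs. The conclusion rests on two assumptions: that key lab personnel include those who run or gate the assays, which is likely but not stated, and that the unavailable section 7 contains no masking provision. If either fails, the remedy reduces to stating the masking arrangement explicitly.

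This is an improvement worth making before samples are read, since masking cannot be restored afterwards.

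**What to change.** Amend sections 8 and 14 so that:

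- Whoever runs and gates the RT-PCR and FACS assays has no access to the index, clinical data, DAS28 status, treatment group or visit until the readouts are final and locked.
- Tubes carry a specimen-level number that shows neither patient nor visit, in place of the subject code.
- The gating template, positivity cut-offs, and rules for repeats and exclusions are written down before any sample is read.
- An existing team member who reads no assays holds the link from specimen number to subject and visit. This may be the principal investigator only if the investigator does not read assays.
- Expression data are merged with DAS28 only after lock.

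Sections 8 and 14 should also use one term for those who may open the key, and say whether it includes assay staff.

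The cost is a small relabelling and access-control burden, and a suspect sample could be checked against clinical data only after lock. Codes, a master list and a separate clinical database already exist, and no patient procedure changes. Section 2 places the analysis in the last year of the project, so linking after lock need not delay it.
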